7.2.2. Summary Measure

Summary statistics (arithmetic mean, geometric mean, median, SD, minimum, maximum, and CV) for urine gepotidacin PK parameter values will be summarized by study day, as appropriate. Gepotidacin urine PK parameter estimates will be listed by participant and study day.

7.2.3. Population of Interest

The secondary PK analyses will be based on the Pharmacokinetic population and Pharmacokinetic Parameter population, unless otherwise specified.

7.2.4. Statistical Analyses / Methods

Details of the planned displays are provided in [Appendix 9: List of Data Displays](#) and will be based on GSK Data Standards and statistical principles.

Unless otherwise specified, endpoints / variables defined in Section [7.2.1](#) will be summarised using descriptive statistics and listed.

7.3. Exploratory Pharmacokinetic Analyses

7.3.1. Endpoint / Variables

7.3.1.1. Drug Concentration Measures

Refer to [Appendix 3: Data Display Standards & Handling Conventions \(Section 12.3.3 Reporting Standards for Pharmacokinetic\)](#).

7.3.1.2. Derived Pharmacokinetic Parameters

Cervical, rectal, and pharyngeal swab specimens for PK analysis of gepotidacin will be obtained Day 4 at predose and at approximately 2 hours postdose. The actual date and time of each sample collection will be recorded. Participation is optional. Participants who do not wish to participate in the tissue PK assessments may still participate in the study. Specific details to ensure a similar physical site of the pharynx is used for swab collection are provided in the Study Reference Manual (SRM) and/or laboratory manual. Collection, processing, storage, and shipping procedures for cervical, rectal, and pharyngeal swab specimens are provided in the SRM and/or laboratory manual.

Summary statistics (arithmetic mean, geometric mean, median, SD, minimum, maximum, and CV) for cervical, rectal, and pharyngeal gepotidacin PK concentration values will be summarized by collection time point, as appropriate. Gepotidacin cervical, rectal, and pharyngeal concentration estimates will be listed by participant and collection time point.

8. SAFETY ANALYSES

The safety analyses will be based on the “Safety” population, unless otherwise specified.

8.1. Adverse Events Analyses

Adverse events analyses including the analysis of AEs, SAEs and other significant AEs will be based on GSK Core Data Standards. All AEs, study drug related AEs, SAEs, and AEs leading to discontinuation of study treatment or withdrawal from study will be provided in separate listings. The relationship between system organ class (SOC) and preferred term (PT) will be listed. Summary tables will be provided for AEs and drug-related AEs by SOC, PT, and maximum grade. Number of subjects and occurrences with common non-serious AEs will be provided in a summary table by SOC.

In summary tables where are presented by SOC, PT, and maximum grade, SOCs will be sorted in descending order of the total incidence then alphabetically, PTs will be sorted in descending order of the total incidence then alphabetically within the SOC.

The details of data displays are presented in [Appendix 9](#): List of Data Displays.

8.2. Clinical Laboratory Analyses

Laboratory evaluations including the analyses of chemistry laboratory tests, hematology laboratory tests, urinalysis, and liver function tests will be based on GSK Core Data Standards.

Summaries of change from baseline values for clinical chemistry and hematology tests will be provided in separate tables. Shift tables for clinical chemistry and hematology results with toxicity grades 2 to 4 will be provided. Urinalysis dipstick results will be summarized using categorical statistics. Clinical chemistry, hematology, and urinalysis test results with toxicity grade 2 or higher will be listed in separate listings.

The details of data displays are presented in [Appendix 9](#): List of Data Displays.

8.3. Other Safety Analyses

The analyses of non-laboratory safety test results including ECGs, vital signs, and liver events will be based on GSK Core Data Standards, unless otherwise specified.

Summary tables will be provided for ECG findings, ECGs change from baseline values, maximum post-baseline QTc values relative to baseline values, and maximum increase in post-baseline QTc values relative to baseline values, vital signs change from baseline values, and worst post-baseline vital signs results relative to baseline results.

Listings will be provided for abnormal ECG findings, ECG values of potential clinical importance, vital sign values of potential clinical importance, liver events, and clostridium difficile results.

The details of data displays are presented in [Appendix 9](#): List of Data Displays.

9. EFFICACY ANALYSES

9.1. Exploratory Efficacy Analyses

The details of data displays being presented in [Appendix 9: List of Data Displays](#).

9.1.1. Endpoint / Variables

- Therapeutic response (combined per-participant microbiological and clinical response) at the TOC Visit
- Microbiological outcome on Days 2 through 5
- Microbiological outcome and response at the TOC and Follow-up Visits
- Sponsor-determined clinical outcome on Days 2 through 5
- Sponsor-determined clinical outcome and response at the TOC and Follow-up Visits
- Investigator-determined clinical outcome on Days 2 through 5 and at the TOC and Follow-up Visits
- Therapeutic response (combined per-participant microbiological and clinical response) at the Follow-up Visit
- Gram stain results at Baseline, Days 2 through 5, TOC, and Follow-up Visits
- Quantitative bacteriology culture results at Baseline, Days 2 through 5, TOC, and Follow-up Visits
- In vitro antimicrobial susceptibility test results at Baseline, Days 2 through 5, TOC, and Follow-up Visits

9.1.1.1. Microbiological Outcome and Response

- The microbiological outcome and response to study treatment will be determined by prespecified programmed algorithm for each participant/qualifying uropathogen.
- The microbiological outcome is determined by comparing the baseline culture results to the culture results at each subsequent visit. The corresponding microbiological response “by qualifying uropathogen” is then assigned. The criteria of microbiological outcome and response are shown in [Table 4](#), [Table 5](#), and [Table 6](#).
- Participant level microbiological success refers to participants who have been deemed a “microbiological success” for all their “qualifying baseline uropathogen” microbiological responses.
- All other combinations are deemed failures for participant level microbiological response.
- Participants who withdraw from the study prior to TOC or Follow-Up Visits will be considered not achieving success as the microbiological response. Microbiological outcome will be derived and listed at early termination visit.
- Microbiological outcome and response along with the 95% Clopper-Pearson CI for the percentage of microbiological response will be summarized for qualifying uropathogens isolated at baseline using the groups listed below at the On-therapy, TOC, and Follow-up visits using counts and percentages. Participant level microbiological response and 95% Clopper-Pearson CI will be summarized within the same table. The necessity of these categories will depend on the uropathogens that are recovered. Any additional uropathogens present in 10 or more participants will be

summarized separately. Additional uropathogens present in less than 10 participants will be grouped into the combined categories (eg, other beta-hemolytic streptococci).

- *Escherichia coli*
 - Quinolone-resistant *E. coli*
 - Extended spectrum beta-lactamase (ESBL) producing *E. coli*
 - Multidrug-resistant (MDR) *E. coli*
- Other gram-negative bacilli
- *Staphylococcus aureus*
- *Staphylococcus saprophyticus*
- Coagulase-negative staphylococci
- Beta-hemolytic streptococci
- Viridans streptococci
- *Enterococcus* spp.
- *Gardnerella vaginalis*
- *Aerococcus urinae*
- Other Gram-positive uropathogens
- A participant will be counted multiple times under an uropathogen category if multiple qualifying uropathogens within that uropathogen category are isolated at baseline for the participant.
- Urine quantitative bacteriology culture results will be summarized and plotted by visit and qualifying uropathogens isolated at baseline

Table 4 Microbiological Outcome by Qualifying Uropathogen at the On-Therapy Visit

Defining Criteria	Outcome

 ● Any participant that receives administration of an alternative or additional antibacterial therapy during the On-Therapy visit will be assigned a microbiological outcome of “unable to determine” from that day onward. 	

 ● A quantitative urine culture taken during the On-Therapy Visit (Days 2 through 5 only) shows that the qualifying bacterial uropathogen recovered at Baseline is reduced to <10³ CFU/mL 	
 ● Microbiological eradication

 ● A quantitative urine culture taken during the On-Therapy Visit (Days 2 through 5 only) shows that the qualifying bacterial uropathogen recovered at Baseline grows ≥10³ CFU/mL 	
 ● Microbiological persistence

 ● A determination of the baseline qualifying bacterial uropathogen microbiological outcome cannot be made (e.g., no urine culture taken, sample lost, etc.) 	
 ● Unable to determine

 ● A new qualifying bacterial uropathogen, not identified at Baseline, is documented by quantitative urine culture during the On-Therapy Visit (Days 2 through 5 only) in a participant who is a sponsor-determined clinical failure or unable to determine 	
 ● Superinfection

Defining Criteria	Outcome

 A new qualifying bacterial uropathogen, not identified at Baseline, is documented by quantitative urine culture at the On-Therapy Visit (Days 2 through 5 only) in a participant who is a sponsor-determined clinical success 	
 Colonization

CFU=colony-forming units

Table 5 Microbiological Outcome and Response by Qualifying Uropathogen at the Test-of-Cure Visit

Defining Criteria	Outcome	Response

 Any participant that receives administration of an alternative or additional antibacterial therapy before the TOC Visit will be assigned a microbiological outcome of “unable to determine” and a response of “microbiological failure”. Participants considered microbiological failures at the TOC Visit will also be considered microbiological failures at the Follow-up Visit. 		

 A quantitative urine culture taken at the TOC Visit shows reduction of the qualifying bacterial uropathogen recovered at Baseline to <10³ CFU/mL 	
 Microbiological eradication 	
 Microbiological success

 A quantitative urine culture taken at the TOC Visit shows that the qualifying bacterial uropathogen recovered at Baseline, and which was also shown to persist at the On-Therapy Visit, grows ≥10³ CFU/mL 	
 Microbiological persistence 	
 Microbiological failure

 A quantitative urine culture taken at the TOC Visit shows that the qualifying bacterial uropathogen recovered at Baseline, and which was also shown to be eradicated at the On-Therapy Visit, grows ≥10³ CFU/mL 	
 Microbiological recurrence 	
 Microbiological failure

 A determination of the baseline qualifying bacterial uropathogen microbiological response cannot be made (e.g., no urine culture taken, sample lost, etc.) 	
 Unable to determine 	
 Microbiological failure

 A new qualifying bacterial uropathogen, not identified at Baseline, is documented by quantitative urine culture at the TOC Visit in a participant who is a sponsor-determined clinical failure 	
 New infection 	
 Microbiological failure

 A new qualifying bacterial uropathogen, not identified at Baseline, is documented by quantitative urine culture at the TOC Visit in a participant who is a sponsor-determined clinical success 	
 Colonization 	
 Microbiological success

CFU=colony-forming units; TOC=Test-of-Cure.

Table 6 Microbiological Outcome and Response by Qualifying Uropathogen at the Follow-Up Visit

Defining Criteria	Outcome	Response

 Any participant that receives administration of an alternative or additional antibacterial therapy before the Follow-up Visit will be assigned a microbiological outcome of “unable to determine” and a response of “microbiological failure”. Participants considered microbiological failures at the TOC Visit will also be considered microbiological failures at the Follow-up Visit. 		

 A quantitative urine culture taken at the Follow-up Visit shows reduction of the qualifying bacterial uropathogen recovered at Baseline to $<10^3$ CFU/mL 	
 Sustained microbiological eradication 	
 Microbiological success

 A quantitative urine culture taken at the Follow-up Visit shows that the qualifying bacterial uropathogen recovered at Baseline grows $\geq 10^3$ CFU/mL 	
 Microbiological recurrence 	
 Microbiological failure

 A determination of the baseline qualifying bacterial uropathogen microbiological response cannot be made (e.g., no urine culture taken, sample lost, etc.) 	
 Unable to determine 	
 Microbiological failure

 A new qualifying bacterial uropathogen, not identified at Baseline, is documented by quantitative urine culture at the Follow-up Visit in a participant who is a sponsor-determined clinical failure 	
 New infection 	
 Microbiological failure

 A new qualifying bacterial uropathogen, not identified at Baseline, is documented by quantitative urine culture at the Follow-up Visit in a participant who is a sponsor-determined clinical success 	
 Colonization 	
 Microbiological success

CFU=colony-forming units; TOC=Test-of-Cure.

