5.4. Scientific Rationale for Study Design

This Phase IIa study is designed primarily to evaluate plasma and urine pharmacokinetics of gepotidacin in participants with acute cystitis. Serial sample collections will be performed on Day 1 (first dose) and on Day 4.

As this PK study will be conducted in female participants with acute cystitis, the exploratory clinical and microbiological efficacy of gepotidacin will also be assessed. The time points and success definitions were based on the Food and Drug Administration (FDA) guidance for industry for developing drug treatments for uncomplicated and complicated UTIs [DHHS, 1998; DHHS, 2015] and the European Medicines Agency (EMA) addendum to the guideline on the evaluation of medicinal products indicated for treatment of bacterial infections [EMA, 2013].

Efficacy will be assessed daily during the On-Therapy Visit, at TOC, and at Follow-up. Clinical success is defined as the resolution of signs and symptoms of acute cystitis present at Baseline (and no new signs and symptoms) and no use of other antimicrobial therapy. Microbiological success is defined as the reduction of the qualifying bacterial uropathogen (defined in [Appendix 9](#)) recovered at Baseline to $<10^3$ colony-forming units (CFU)/mL as observed on quantitative urine culture. Therapeutic success refers to participants who have been deemed both a microbiological success and a clinical success (i.e., responders).

Adult (≥ 18 to ≤ 65 years of age) eligible female participants will be enrolled in this open-label Phase IIa PK study. This age range was selected to minimize variability in systemic exposures as well as baseline uropathogens. This study in acute cystitis is restricted to female participants per the FDA guidance [DHHS, 1998]. As described in [Section 5.5](#), the dose of gepotidacin and the 5-day duration were selected to provide efficacious treatment for acute cystitis and is in alignment with current clinical practice.

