9.1.2.1. Microbiological Outcome and Response

Only those participants who have a qualifying bacterial uropathogen (defined in [Appendix 9](#)) identified at Baseline will be evaluated for microbiological outcome and response. The microbiological outcome and response to study treatment will be determined by prespecified programmed algorithm for each participant/pathogen.

The microbiological outcome is determined by comparing the baseline culture results to the culture results at each subsequent visit (see [Table 3](#), [Table 4](#), and [Table 5](#)). The corresponding microbiological response (success or failure) “by pathogen” is then assigned, as shown in [Table 4](#) and [Table 5](#). Participant level microbiological response is a measure of the combined “by pathogen” response(s). Participant level microbiological success refers to participants who have been deemed a “microbiological success” for all of their “by pathogen” microbiological responses. All other combinations (other than all “microbiological successes”) are deemed failures for participant level microbiological response. Participant level microbiological response will be determined by statistical programming.

Table 3 Microbiological Outcome by Pathogen at the On-Therapy Visit

Defining Criteria	Outcome

 Any participant that receives administration of an alternative or additional antibacterial therapy during the On-Therapy Visit will be assigned a microbiological outcome of "unable to determine" from that day onward. 	

A quantitative urine culture taken during the On-Therapy Visit (Days 2 through 5 only) shows that the qualifying bacterial uropathogen recovered at Baseline is reduced to $<10^3$ CFU/mL
	Microbiological eradication

A quantitative urine culture taken during the On-Therapy Visit (Days 2 through 5 only) shows that the qualifying bacterial uropathogen recovered at Baseline grows $\geq 10^3$ CFU/mL
	Microbiological persistence

A determination of the baseline qualifying bacterial uropathogen microbiological outcome cannot be made (e.g., no urine culture taken, sample lost, etc.)
	Unable to determine

A new qualifying bacterial uropathogen, not identified at Baseline, is documented by quantitative urine culture during the On-Therapy Visit (Days 2 through 5 only) in a participant who is a clinical failure or unable to determine
	Superinfection

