
A new qualifying bacterial uropathogen, not identified at Baseline, is documented by quantitative urine culture at the On-Therapy Visit (Days 2 through 5 only) in a participant who is a clinical success
	Colonization

CFU=colony-forming units.

Table 4 Microbiological Outcome and Response by Pathogen at the Test-of-Cure Visit

Defining Criteria	Outcome	Response

 Any participant that receives administration of an alternative or additional antibacterial therapy before the TOC Visit will be assigned a microbiological outcome of "unable to determine" and a response of "microbiological failure." Participants considered microbiological failures at the TOC Visit will also be considered microbiological failures at the Follow-up Visit. 		
A quantitative urine culture taken at the TOC Visit shows reduction of the qualifying bacterial uropathogen recovered at Baseline to $<10^3$ CFU/mL	Microbiological eradication	Microbiological success
A quantitative urine culture taken at the TOC Visit shows that the qualifying bacterial uropathogen recovered at Baseline, and which was also shown to persist at the On-Therapy Visit, grows $\geq 10^3$ CFU/mL	Microbiological persistence	Microbiological failure
A quantitative urine culture taken at the TOC Visit shows that the qualifying bacterial uropathogen recovered at Baseline, and which was also shown to be eradicated at the On-Therapy Visit, grows $\geq 10^3$ CFU/mL	Microbiological recurrence	Microbiological failure
A determination of the baseline qualifying bacterial uropathogen microbiological response cannot be made (e.g., no urine culture taken, sample lost, etc.)	Unable to determine	Microbiological failure
A new qualifying bacterial uropathogen, not identified at Baseline, is documented by quantitative urine culture at the TOC Visit in a participant who is a clinical failure	New infection	Microbiological failure
A new qualifying bacterial uropathogen, not identified at Baseline, is documented by quantitative urine culture at the TOC Visit in a participant who is a clinical success	Colonization	Microbiological success

CFU=colony-forming units; TOC=Test-of-Cure.

Table 5 Microbiological Outcome and Response by Pathogen at the Follow-Up Visit

Defining Criteria	Outcome	Response

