2.1. Changes to the Protocol Defined Statistical Analysis Plan

Changes from the originally planned statistical analysis specified in the protocol are outlined in [Table 1](#).

Table 1 Changes to Protocol Defined Analysis Plan

Protocol	Reporting & Analysis Plan	
Statistical Analysis Plan	Statistical Analysis Plan	Rationale for Changes

 Clinical outcome will be determined by the investigator 	
 In addition to investigator-determined clinical outcome, a sponsor-determined clinical outcome will be programmatically derived 	
 To solve the potential dilemma that a participant with record missing or unable-to-determine at Test-of-Cure (TOC) visit but free of signs and symptoms of acute cystitis at Follow-up Visit will likely be determined as “clinical success” by the investigator but falls under failure per US Food and Drug Administration (FDA) guidance [DHHS, May 2018; DHHS, June 2018].

 Clinical outcome will be determined at the On-Therapy (Days 2 through 5), TOC, and Follow-up visits by comparing the signs and symptoms of acute cystitis to those present at Baseline. Clinical response (success or failure) will be determined at the TOC and Follow-Up visits 	
 In addition, clinical cure, a binary result of ‘Yes’ or ‘No’ will be determined at the On-Therapy (Days 2 through 5), TOC, and Follow-Up visits. Clinical cure is defined as complete resolution of signs and symptoms of acute cystitis present at Baseline, with no new signs and symptoms, and no use of other antimicrobial therapy. Clinical cure at Follow-up visit must also meet clinical cure at TOC in addition to above criteria 	
 To apply a clinical criterion that is consistently focusing on complete resolution of clinical signs and symptoms through On-Therapy, TOC, and Follow-Up visits.

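### SAP 9.1.1.1 limits participant-level microbiological success to baseline uropathogens, an undeclared change from protocol 9.1.2.1 that can turn a participant-level failure into a success

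*SAP*

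**What the plan says.** **Protocol.** Section 9.1.2.1 builds the participant-level result from the by-pathogen responses. Success needs success "for all of their “by pathogen” microbiological responses"; all other combinations "are deemed failures for participant level microbiological response". Among the by-pathogen rows of protocol Table 4 is a new qualifying uropathogen, absent at Baseline, that is "documented by quantitative urine culture at the TOC Visit in a participant who is a clinical failure". Its outcome is New infection and its response is microbiological failure. Protocol Table 5 has the matching row for Follow-up.

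Protocol 5.4, the design rationale, is worded differently: "Microbiological success is defined as the reduction of the qualifying bacterial uropathogen" found at Baseline to below 10^3 CFU/mL. It does not mention new pathogens.

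**SAP.** Section 9.1.1.1 requires success "for all their “qualifying baseline uropathogen” microbiological responses". SAP Table 5 keeps the New infection row (a new pathogen "documented by quantitative urine culture at the TOC Visit in a participant who is a sponsor-determined clinical failure") and still rates it a microbiological failure. SAP Table 6 does the same for Follow-up. Both tables keep the carry-forward statement that a microbiological failure at TOC remains one at Follow-up. Table 6 also makes anyone who received another antibacterial before Follow-up a failure.

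SAP 2.1 states: "Changes from the originally planned statistical analysis specified in the protocol are outlined in" its Table 1. That table has two entries, the sponsor-determined clinical outcome and clinical cure. Neither concerns the microbiological roll-up.

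**The concern.** A New infection is by definition a pathogen not present at Baseline, so it cannot be among the responses that the SAP rule counts. The New infection rows in SAP Tables 5 and 6 therefore have no effect on the participant-level result, whereas under protocol 9.1.2.1 they do.

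Microbiological response at TOC and Follow-up is an endpoint in its own right in protocol Section 4 and SAP 9.1.1, and the SAP gives the participant-level rate its own Clopper-Pearson interval. The by-pathogen summary in SAP 9.1.1.1 and display Table 2.1 is organised by the uropathogens isolated at Baseline. The participant-level line is thus the place in that table where a New infection would register as a failed response.

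The difference also runs one way. The SAP rule is the protocol rule with a condition removed, so it can raise the rate but never lower it.

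**Working it through.** Neither document gives a figure to reproduce, so the check applies both rules to the same cases.

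**1. The rules side by side**

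- Protocol 9.1.2.1: success = all baseline-pathogen responses succeed AND all new-pathogen responses succeed.
- SAP 9.1.1.1: success = all baseline-pathogen responses succeed.

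**2. All TOC combinations**

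Inputs, from protocol Tables 4 and 6 and SAP Tables 5 and 7:

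- baseline pathogen: eradicated, grows, or unable to determine (3)
- new qualifying pathogen: no or yes (2)
- clinical outcome: success, failure, or unable to determine (3)
- other antibacterial before TOC: no or yes (2)

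This gives 3 × 2 × 3 × 2 = 36. Clinical success together with other antibacterial use is excluded (3 × 2 = 6), which leaves 30.

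| Baseline pathogen | New pathogen | Clinical outcome | Other antibacterial | Response for new pathogen | Protocol 9.1.2.1 | SAP 9.1.1.1 | Therapeutic response |
|---|---|---|---|---|---|---|---|
| Eradicated | No | Success | No | – | Success | Success | Success in both |
| Eradicated | No | Failure or unable to determine | No | – | Success | Success | Failure in both |
| Eradicated | Yes | Success | No | Colonization: success | Success | Success | Success in both |
| **Eradicated** | **Yes** | **Failure** | **No** | **New infection: failure** | **Failure** | **Success** | **Failure in both** |
| Eradicated | Yes | Unable to determine | No | None assigned | Success | Success | Failure in both |
| Grows or unable to determine | Any | Any | Any | Any | Failure | Failure | Failure in both |
| Eradicated | Any | Failure or unable to determine | Yes | Any | Failure | Failure | Failure in both |

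The participant-level result differs in 1 of 30 combinations and therapeutic response in 0 of 30. Therapeutic response cannot move because a New infection requires clinical failure.

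The count rests on two assumptions. First, the clinical determination is the same under both rules and for therapeutic response. Second, a new pathogen at TOC in a participant whose clinical outcome is unable to determine carries no response, because neither TOC table assigns one. If it were rated a failure, that combination would differ too.

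**3. Follow-up**

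SAP Table 6 has the same structure. For a participant in the bold row, the SAP does not say whether the carry-forward acts on the by-pathogen failure, which exists, or on a participant-level failure, which under the SAP rule does not. If another antibacterial is given before Follow-up, the participant is a failure there under both documents.

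**4. Size**

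Each affected participant shifts the rate by 1/n. The Clopper-Pearson limits for x of n are the 2.5% quantile of Beta(x, n − x + 1) and the 97.5% quantile of Beta(x + 1, n − x); the upper limit is 100% when x = n. The micro-ITT sizes, the success counts and the single affected participant are all assumptions.

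| n | SAP rule (95% CI) | Protocol 9.1.2.1 rule (95% CI) | Shift (points) |
|---|---|---|---|
| 8 | 7/8 = 87.5% (47.3–99.7) | 6/8 = 75.0% (34.9–96.8) | 1/8 = 12.5 |
| 12 | 12/12 = 100% (73.5–100) | 11/12 = 91.7% (61.5–99.8) | 1/12 = 8.3 |
| 15 | 13/15 = 86.7% (59.5–98.3) | 12/15 = 80.0% (51.9–95.7) | 1/15 = 6.7 |
| 25 | 21/25 = 84.0% (63.9–95.5) | 20/25 = 80.0% (59.3–93.2) | 1/25 = 4.0 |

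**The case against.** The strongest defence is that the protocol is not uniform. Section 5.4 defines microbiological success by the baseline pathogen alone, and 9.1.2.1 itself derives outcomes by comparing later cultures with the baseline culture. On that view the SAP follows one protocol definition rather than departing from the protocol. Little also depends on the point: efficacy is exploratory and no hypothesis is tested. New pathogens are not hidden either, since display Tables 2.3 and 2.4 include qualifying uropathogens that emerge after Baseline and Listing 14 gives the culture results.

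The inconsistency is real, so the SAP cannot be said to contradict every protocol definition. But 5.4 is rationale, while 9.1.2.1 with its tables is the operational rule. Read as baseline-only, the protocol's New infection rows would also have no participant-level effect. The MIC tables and the culture listing show the organism, not a failed response. The low stakes limit the size of the point but do not excuse leaving the change undeclared.

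Three stronger readings are tempting, and the documents do not support them:

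- A reader might infer that the SAP reclassifies a New infection as a success. It does not. Tables 5 and 6 still rate it a failure, and only the roll-up to the participant changes.
- A reader might infer that every symptomatic participant with a new uropathogen counts as a success. Both documents give failure if any baseline pathogen grows or cannot be determined, or if another antibacterial was given before TOC.
- A reader might infer that the carry-forward is gone, so that the Follow-up rate is inflated as well. The statement is still in the SAP, and its application here is unclear rather than lost. Protocol 9 leaves treatment of new or continuing symptoms to the investigator, so some of these participants may be Follow-up failures anyway through antibacterial use.

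**Conclusion.** The point holds in a limited form. SAP 9.1.1.1 makes an undeclared change to the participant-level rule of protocol 9.1.2.1. At TOC it alters the result for one kind of participant, always from failure to success. It also leaves the SAP's own New infection rows without participant-level effect.

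The reach is the exploratory participant-level microbiological response at TOC, and possibly at Follow-up. The PK/PD displays (Table 5.1, Figure 5.1) split by microbiological success and failure, and are affected only if they use the participant-level result. Therapeutic response at both visits and the primary plasma PK endpoints are untouched.

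The shift is 1/n per affected participant, between 4.0 and 12.5 points over the assumed sizes of 25 down to 8. If no such participant occurs, it is zero. The change is worth making because the endpoint has its own interval, the error has one direction, and two programmers could code the present text differently.

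**What to change.** In SAP 9.1.1.1, restore the protocol 9.1.2.1 rule: participant-level success requires success on every by-pathogen response at the visit, so that a New infection response is a participant-level failure at TOC and at Follow-up. State that the TOC carry-forward applies to it. Report participant-level eradication of all baseline uropathogens, the protocol 5.4 definition, as a separate row in display Table 2.1. The by-pathogen eradication rows already planned there stay as they are.

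If the baseline-only rule is intended, list it in SAP Table 1 with a reason, and say how the New infection and carry-forward rows of Tables 5 and 6 then apply.

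The cost is one sentence and one table row, with no new data. The reported participant-level rate may be slightly lower.
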